#### 1.2 Investigational Product (IP)

An investigational product is defined as a pharmaceutical form of an active substance or placebo being tested or used as a reference in a clinical study, including products already with a marketing authorization but used or assembled (formulated or packaged) differently than the authorized form, or used for an unauthorized indication, or when used to gain further information about the authorized form. The investigational products will be stored in a secure area according to local regulations. Investigators will have responsibility for ensuring that investigational product is only dispensed to study subjects. The investigational products (Fisetin and placebo) will be dispensed only by authorized personnel according to regulations that apply at pharmacies associated with the subjects' nursing homes, Mayo Clinic Rochester and the other Translational

Geroscience Network (TGN) sites. In this protocol, the investigational products are Fisetin and placebo.

**Fisetin:** Fisetin (3,3',4',7-tetrahydroxyflavone) is a member of the flavonoid family, a family of naturally-occurring polyphenolic compounds. As a natural product, it is widely sold, including by Amazon, from which it is available in containers of 30 capsules of 100 mg Fisetin/ capsule at <\$20 per container and also containers of 500 mg capsules. The structure of Fisetin is similar to that of Q, which is one of the first two senolytic drugs discovered (Fig. 10). Fisetin (Fig. 11), a high Trolox-equivalent antioxidant, is present in many fruits and vegetables such as apples, persimmon, grapes, onions, and cucumbers, with the highest concentration found in strawberries (160  $\mu$ g/g). The average dietary intake of naturally-occurring Fisetin was approximately 0.8 mg/day in an earlier Japanese study. However, the average total intake of polyphenols, comprised mainly of flavonoids, is around 1 gram per day, although it may be quite variable. Fisetin has little or no odor or taste.

но он он

Fig. 10. Structure of the senolytic flavonol, Q. Quercetin, one of the first two senolytic drugs identified (along with Dasatinib [D]), and which is present in apple peels, has a bitter taste and is less bioavailable and has a longer elimination T½ than Fisetin.

Fig. 11. Structure of Fisetin. Fisetin differs from Q by a hydroxyl group. It has little or no odor or taste. Its terminal T½ in mice is ~3.1 hrs¹. This short half-life makes Fisetin ideal as a senolytic drug to ablate pro-inflammatory, pro-apoptotic, non-dividing senescent cells in a "hit-and-run" fashion8. Fisetin 100 and 500 mg capsules have been widely sold by Amazon and other vendors and have caused no proven side effects in over-the-counter sales in any reports that we can find.

Due to its being a hydrophobic compound, Fisetin easily penetrates cell membranes, entering into cells to exert antioxidative and other effects. Other promising biological activities include anti-hyperlipidemic, anti-inflammatory, neurotrophic, apoptotic, and antiproliferative effects.

There are reports of genotoxicity due to some flavonols, but Fisetin may exert little or no genotoxic effects *in vivo*. Indeed, Fisetin has been noted to be anticarcinogenic. We found that chronic Fisetin administration delays cancer in mice and increases remaining lifespan in old mice by over 17%. Since up to 50% of most mouse strains die from cancers, this suggests that the beneficial effects of Fisetin on such carcinogenic factors as senescent cell burden and tissue chronic inflammation more than counteract any theoretical effects of flavonol-associated genotoxicity. In the same mouse study, Fisetin was administered to a murine model of a human progeroid syndrome. These mice are profoundly sensitive to genotoxic agents, yet their health and lifespan were improved by long-term, high dose Fisetin. *Thus, Fisetin is anti-carcinogenic*.

Fisetin is available as a dietary supplement. Other flavonols such as Q have been safely used in clinical trials in amounts up to 500 mg twice daily for up to 8 weeks. To date, no reports of significant toxicity for Fisetin *in vivo* have been made. Since Fisetin, along with other flavones and flavonoids, has been shown to inhibit cytochrome P450 2C9, CYP3A4, and others (Section 3.9.4), precaution will be taken to avoid significant drug-drug interactions, *e.g.*, with warfarin.

We demonstrated that Fisetin is a senolytic agent and alleviates multiple senescence-associated disorders in mice, decreases physical dysfunction if administered to old mice, attenuates agerelated tissue damage and pathology, and extends remaining lifespan by 17%. We have not found any adverse effects in mice (at up to 25 times the dose used in the mouse effectiveness studies [below] or the dose for humans proposed here) or old *Rhesus* monkeys (at up to 5 times the dose for humans proposed here). We obtained a full IND for Fisetin from the FDA and have a GMP drug supply handled by Mayo Research Pharmacy. We are currently conducting a clinical trial of Fisetin *vs.* placebo in elderly subjects with multi-morbidity and impaired mobility living in the community but without CoV to alleviate frailty, AFFIRM (Alleviation by Fisetin of Frailty, Inflammation, and Related Measures in Older Adults; ClinicalTrials.gov identifier NCT03430037; IND 134052; >50 subjects enrolled; no severe or serious adverse events so far).

Here, Fisetin 100 mg capsules or Fisetin (with cellulose) powder (in water, other chilled or room-temperature drinks, apple sauce, pudding, yogurt, or enteral hydration/ nutrition solutions) vs. placebo will be administered orally or by NG or D tube (~20 mg/ kg/ day) twice for 2 consecutive days on study Days 0, 1, 8, and 9 to elderly CoV positive nursing home residents (by mRNA-PCR within 10 day prior to randomization). To reduce senescent cell abundance by a "hit-and-run" approach, the full daily doses of Fisetin will be administered within 30 minutes. The investigational supplies will be obtained from Vital Nutrients, a contracted GMP manufacturer. Fisetin capsules supplied by Vital Nutrients are opaque blue in color. Fisetin powder is a green yellow color. We established stability parameters for Fisetin in collaboration with Mayo Clinic's Department of Laboratory Medicine and Pathology. We acquired an IND for Fisetin after establishing botanical sourcing, GMP isolation by Vital Nutrients, assurance of lack of contaminating pesticides, heavy metals, and solvents, and stability and degradation. We are currently conducting a clinical trial of Fisetin vs. placebo in hospitalized, non-ventilated elderly CoV patients to prevent progression of respiratory dysfunction, COVID-FISETIN (A Phase 2 Placebo-Controlled Pilot Study in COVID-19 of Fisetin to Alleviate Dysfunction and Excessive Inflammatory Response in Hospitalized Older Adults; IND 149813).

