**Fig. 26.** Fisetin treatment slows death of old mice infected with β-coronavirus. (A) Male 24 month old mice were transported from Mayo Clinic to the mouse β-coronavirus contaminated colony at U of M, depicted here as Day 0. All mice were exposed to bedding used by infected male mice. Beginning 3 days after transfer from Mayo Clinic, they were treated for 3 days with Fisetin 20 mg/kg/day as daily pulse doses vs. vehicle by oral gavage (N=10 mice/ group) on Days 4 to 6. On Days 7 to 9, the Fisetin-treated mice were fed with chow containing Fisetin 500 ppm and the vehicle-treated mice were fed chow only. On Days 10 to 12 and 13 to 16, animals were treated with Fisetin 20 mg/kg as daily pulse doses vs. vehicle by oral gavage on Days 10 to 12 and 13 (all vehicle-treated mice were dead at Day 14). On Day 17 animals were treated with Fisetin 20 mg/kg as daily pulse doses. (B) Female 24 month old mice were treated in the same way. Fisetin significantly increased survival of β-coronavirus-infected mice (males: p < 0.0001; females: p < 0.0001; log-rank Mantel Cox test).

Fisetin treatment of old,  $\beta$ -coronavirus-infected male as well as female mice slowed death (Fig. 26). Similarly, targeting  $p16^{lnk4a}$ -expressing cells, many of which are senescent, by treating old MHV-infected lnK-ATTAC mice with AP20187, delayed death (Fig. 27). Of note, in separate, parallel studies in which animals were euthanized after cohousing or exposure to dirty bedding, transmission of MHV was 100% and antibodies against the virus were detected by day 11 (Fig. 23). No antibodies to other common mouse pathogens were detectible. Additionally, only 2 days Fisetin significantly decreased mortality in old female mice infected by  $\beta$ -coronavirus (Fig. 28). Mortality began to increase at Day 7, leading us to test 2 courses of 2 days Fisetin (Fig. 29).

[figure not shown]
[figure not shown]

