# 4 Subject Selection, Enrollment, and Withdrawal

#### 4.1 Inclusion Criteria

Subjects must meet *all* of the following inclusion criteria to be eligible for enrollment:

- 1. Men or post-menopausal women age  $\geq$ 65 years.
- 2. Current nursing home resident.
- 3. CoV severity of moderate or less OR SpO2  $\geq$  85% (on room air or  $\leq$  2 L of supplemental oxygen) at time of enrollment.
- 4. SARS-CoV-2 infection confirmed by mRNA-PCR test at Mayo Clinic or other CLIA certified laboratory, within 10 days before randomization.
- 5. Willing and able to provide written informed consent or have a legally authorized representative (LAR) who will provide informed consent.

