# 6.1 Screening Visit (Days -2 to 0)

Patients will be pre-screened prior to being recruited for the study. Subjects will be screened within 3 days before randomization to determine eligibility for participation in the study.

Written informed consent will be obtained from the nursing home resident or from a Legally Authorized Representative (LAR) who can provide informed consent. Sections B to E (B: Hearing, Speech, and Vision, C: Cognitive Patterns, including the Brief Interview for Mental Status, D: Mood, and E: Behavior) of the most recent (within the last 100 days) Minimum Data Set (MDS) will be utilized to determine participants' ability to provide a truly informed consent and such an ability should be verified by staff with access to the nursing homes (e.g., Medical or Nursing Director, nurse practitioner, physician's assistant) and if the participant is not able, their LAR will be asked. All MDS datasets for each subject will be collected throughout their inclusion in the study (up to 194 days) and the date(s) and type of vaccinations for CoV will be recorded.

In the pandemic situation where access to nursing homes and hospitals is limited, if allowed, digital/electronic consent will be obtained from the patient's LAR and will be documented by the investigator or the authorized designee. For any subject, it is the responsibility of the investigator or study team member to obtain consent prior to performing any protocol-mandated assessment.

After the informed consent and agreement by the patient's nursing home attending physician, nurse-practitioner, or physician's assistant, the following assessments are performed to determine eligibility requirements as specified in the inclusion and exclusion criteria. Assessments performed as part of the routine care of the subject by nursing home staff may be used to assess eligibility.

- Demographics.
- Focused medical history including the following information if feasible: date of first symptoms, overall symptoms, exposure source, demographics, baseline characteristics, allergies, medical history, reasons for nursing home admission (diagnoses, key symptoms and signs at and since admission as abstracted from the most recent MDS or available nursing home records).
- Determination of Ordinal Scale score.
- Review of concomitant medications including any COVID-19 vaccinations.
- Review of adverse events.

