# 8 Statistical Plan

### 8.1 Sample Size Determination

Power calculations for the comparison of the Fisetin and control groups were made assuming an equal distribution among the 7-point scale categories at Day 14 among the controls using a two-sided significance level of 0.05 (alpha). With 75 subjects per group, the study would have 80% power to detect a log odd's ratio of 0.81 which translates to an odd's ratio of 2.25 comparing the control to Fisetin group. Power calculations were run using the PASS software package.

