#### 8.2 Statistical Methods

All participants who are randomized will be included in the primary efficacy analysis. The analysis will follow the ITT principle (*i.e.* according to the treatment arm they are randomized to). For the primary analysis using the values of the 7-point scale, we will test the coefficient of the treatment effect (as a fixed effect) in an ordinal logistic regression model using a 2-sided 0.05 level Wald test after adjusting for key baseline variables such as baseline COVID severity status, age, and sex that show imbalance between the groups. Subjects who withdraw early but received at least some treatment will have their last known values carried forward until they complete the study at Day 180±14. All participants who receive any dose of drug (Fisetin or placebo) will be included in the safety and tolerability evaluation. The definitions of adverse events are described in Sections 9.1-9.3. Participants will be assessed over the entire period of drug administration. Frequency tables will be generated to summarize the occurrence of AE's by treatment arm. Comparisons of the rates of individual AEs will be done using tests of proportions such as the Fisher's exact test or Chi-squared test.

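### Days from the qualifying positive PCR to randomization (0 to 10) can be derived for everyone correctly enrolled, but no analysis prespecifies this interval as a covariate or effect modifier

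*Combined protocol and SAP*

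**What the plan says.** Section 4.1 requires "SARS-CoV-2 infection confirmed by mRNA-PCR test at Mayo Clinic or other CLIA certified laboratory, within 10 days before randomization". Section 1.2 repeats the window when it describes who will be treated: "CoV positive nursing home residents (by mRNA-PCR within 10 day prior to randomization". Section 6.1 asks for dosing on the day of randomization only where possible, so the 10 days limit randomization and not the first dose.

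Section 5.3 randomizes in permuted blocks with no stratification. Section 8.2 tests one treatment coefficient in an ordinal logistic model, "adjusting for key baseline variables such as baseline COVID severity status, age, and sex that show imbalance between the groups". In the secondary plan, the rate and time-to-event models adjust for further factors that are not named. The paragraph on factors and interactions names only age, sex, race and ethnicity.

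Two dates bear on stage of illness. The qualifying PCR date is needed to verify eligibility. Symptom onset is collected less firmly: "Focused medical history including the following information if feasible: date of first symptoms". Section 7.2 also lets a PCR be ordered for research purposes after consent, so the qualifying test need not be the resident's first positive one.

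**The concern.** The primary objective is to prevent or delay progression, so how much of the illness lies ahead at randomization plausibly affects the Day 14 score. Two residents with the same baseline score, one tested today and one ten days ago, may not face the same remaining risk.

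Two things could follow. First, if the interval predicts outcome beyond baseline severity, leaving it out of an ordinal logistic model pulls the treatment odds ratio towards 1 and forgoes some power, even with balanced arms. Second, if the treatment effect depends on stage, a single coefficient averages it, and any later look by interval would be post hoc. Section 3.1 presents this pilot as the rationale for larger trials, whose eligibility windows would depend on that answer.

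**Working it through.** **1. Timing.** With randomization on Day 0, Day 14 falls at 0 + 14 = 14 to 10 + 14 = 24 days after the qualifying test, before the ±2-day visit window.

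**2. The plan's own power.** Inputs from section 8.1: a two-sided alpha of 0.05, controls spread equally over seven categories, and this target: "With 75 subjects per group, the study would have 80% power to detect a log odd's ratio of 0.81". On the odds-ratio scale, section 8.1 gives the target as 2.25.

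Whitehead's formula for proportional odds with 1:1 allocation is N = 12(z₀.₉₇₅ + z₀.₈₀)² / [(ln OR)² (1 − Σp̄ᵢ³)], where p̄ᵢ is the mean of the two arms' probabilities in category i.

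- ln 2.25 = 0.811. With controls at 1/7 each, Σp̄ᵢ³ = 0.024.
- N = 12 × 7.849 / (0.658 × 0.976) = 147, against 150 planned.
- At N = 150, SE = √[12 / (150 × 0.976)] = 0.286. Power = Φ(0.811/0.286 − 1.96) = 80.9%.
- At the Study Summary's odds ratio of 2.24, power is 80.4%.

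The stated 80% reproduces. It is for a treatment odds ratio with no covariates.

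**3. What adjustment would change.** The documents give no prognostic strength for the interval, so a range is assumed. The simulation model is logit P(Y ≤ k) = αₖ + γ(t − 5) + β·treatment, with t uniform on 0 to 10 days, β = ln 2.25 and 75 per arm. The αₖ are set so that controls average 1/7 per category. A two-sided 0.05 Wald test was used, with 4,000 runs per row. The interval's odds ratio across the window is exp(10γ).

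| Interval OR, day 0 to 10 (assumed) | Power unadjusted | Power adjusted | Unadjusted treatment OR |
|---|---|---|---|
| 1 (none) | 80.1% | 79.8% | 2.27 |
| 1.5 | 80.0% | 79.9% | 2.27 |
| 2 | 80.2% | 81.2% | 2.27 |
| 4 | 76.5% | 79.4% | 2.20 |
| 9 | 71.6% | 79.0% | 2.11 |

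Monte Carlo error is about 0.6 to 0.7 points per entry; both fits in a row use the same simulated data. With no treatment effect (2,000 runs), rejection was 5.6% unadjusted and 5.3% adjusted.

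**4. If the effect fades with the interval (hypothetical).** Interval not otherwise prognostic, 2,000 runs each, Monte Carlo error up to about 1.1 points.

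- OR 2.25 at day 0 falling to 1 at day 10: mean log OR = 0.811 × 0.5 = 0.405, so the pooled OR is about exp(0.405) = 1.50. Approximate power is Φ(0.405/0.286 − 1.96) = 29%. Simulated power is 28.1% unadjusted and 28.5% adjusted.
- OR 2.25 on days 0 to 5 and 1 on days 6 to 10: mean log OR = 0.811 × 6/11 = 0.442, so the pooled OR is about 1.56. Simulated power is 33.4% and 34.0%.
- Power of a treatment-by-interval test is 14% in the first case and 23% in the second. It is 43% if the OR runs from 2.25² = 5.06 down to 1.

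**The case against.** The strongest reply is that nothing planned is lost. Section 8.1 powers an odds ratio with no covariates, that quantity is a legitimate target, and its 80% reproduces. A reader might infer from the missing covariate that the stated power is too high. The documents do not support that: the shortfalls in the table arise only when 2.25 is treated as the odds ratio conditional on the interval. What adjustment offers is a possible gain. That gain depends on what the interval adds beyond baseline severity, which section 8.2 already names and which the simulation leaves out. All of this stands.

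The covariate list is introduced by such as, so the interval could still be added. This also stands: the gap is in prespecification, and section 8.2 does not rule the interval out.

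A reader might also take the mouse experiments in section 1.3 as evidence that late dosing fails. They do not show it. Post-infection dosing there began about three days after exposure, and no late-start arm is described. The sentence "Mortality began to increase at Day 7, leading us to test 2 courses of 2 days Fisetin (Fig. 29" follows a single two-day course, and section 1.5 uses that later rise to justify the second course. The experiments make timing relevant; they do not establish stage dependence.

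Finally, time since a test is a weak marker of stage. A research PCR can give a late-stage resident an interval near zero, and residents without symptoms are eligible. This limits the covariate's value but does not remove it.

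**Conclusion.** The gap is real and modest. The interval can be derived for every correctly enrolled participant, yet no stratification, named covariate or planned interaction uses it. Adjusting would change power by about 1 point or less if the interval's odds ratio across the window is 2 or below. The gain would be about 3 points at 4 and about 7 at 9, and adjustment costs almost nothing if the interval is not prognostic. These figures rest on an assumed uniform interval, assumed prognostic strengths and a conditional treatment odds ratio of 2.25.

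It would be tempting to conclude that the trial has only about 29% power because of the window. That figure needs an early-only effect, which the documents do not show, and the covariate leaves it unchanged. For that scenario the useful remedy is a prespecified estimate by interval. A significance test at N = 150 would usually miss the pattern.

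**What to change.** In section 8.2, state that the primary ordinal model includes days from the qualifying PCR to randomization (continuous) as a fixed covariate, whether or not it is imbalanced, alongside baseline severity. Define it to randomization and not to first dose: time to first dose is settled after randomization and is undefined for anyone randomized but never dosed, whom the intention-to-treat analysis includes.

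In the secondary plan, prespecify one supportive treatment-by-interval estimate with its 95% confidence interval. Label it exploratory and state its low power (about 14% to 23% in the two cases where an early odds ratio of 2.25 gives way to 1).

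Add a sensitivity analysis using date of first symptoms where known, because a research PCR may be the qualifying test.

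The cost is a few sentences and one extra parameter in the primary model, with no new data. The limitation to state is that the interval is an imperfect marker of disease stage.

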#### 1.3 Preclinical Data

In our article about the first senolytics discovered, we demonstrated D+Q reduces senescent cell burden in multiple tissues and improves function in naturally-aged animals. Since then, D+Q, Fisetin (which is closely related to Q), Navitoclax, and other senolytics have been shown to alleviate multiple diseases and disorders in animal models (Table 1). Among effects are: restoration of mesenchymal stem cell (MSC) function; improved cardiac ejection fraction, fractional shortening, and regeneration in old mice; enhanced vascular reactivity in old mice, decreased vascular calcification and restored vascular reactivity in hypercholesterolemic, high fat-fed  $ApoE^{-/-}$  mice; decreased loss of intervertebral disc glycosaminoglycans and spondylosis in progeroid  $Ercc I^{-/-/-}$  mice; decreased gait disturbance in mice following radiation damage to a leg and hematological dysfunction caused by whole body radiation; decreased age-related changes in skin; improved pulmonary function and reduced pulmonary fibrosis in mice with bleomycininduced lung damage, a model of IPF, plus decreases in: liver fibrosis in  $Mdr^{-/-}$  cirrhotic mice; hepatic steatosis, insulin resistance, and renal dysfunction in high fat-fed mice; neuropsychiatric dysfunction and impaired neurogenesis in high fat-fed mice; neuro-inflammation, impaired

neurogenesis, microvascular impairment, and cognitive dysfunction in mouse models of dementia; age-related osteoporosis; uterine fibrosis; physical frailty; and muscle weakness in naturally-aged, progeroid, radiated, and senescent cell-transplanted young mice, as well as delayed cancer and increased healthspan and lifespan in old mice.

Condition	Reference
Dishered Obseits	S 27,67,70-73
Diabetes/ Obesity	62,63,74
Cardiac Dysfunction	63
Vascular Hyporeactivity/ Calcification	75
AV Fistulae	
Frailty	25,38,59,64
Age-Related Muscle Loss (Sarcopenia)	76
Chemotherapy Complications	25,31,42,64,77
Radiation Complications	78
Cancers	25
Bone Marrow Transplant Complications	31
Organ Transplantation Complications	24,79
Myeloma/ MGUS	80
Age-Related Cognitive Dysfunction	81
Alzheimer's Disease	82,83
Parkinson's Disease	84
Amyotrophic Lateral Sclerosis	85
Ataxia	38
Obesity-Related Neuropsychiatric Dysfunction	86
Renal Dysfunction	87,88
Urinary Incontinence	38
Osteoporosis	89-91
Osteoarthritis	92
Age-Related Intervertebral Disk Disease	38,93
Idiopathic Pulmonary Fibrosis	64,94
Hyperoxic Lung Damage	95
Chronic Obstructive Pulmonary Disease	96
Tobacco	97
Hepatic Steatosis	66
Cirrhosis	65
Primary Biliary Cirrhosis	98
Progerias	38,59
Pre-eclampsia	99
Macular Degeneration	100,101
Glaucoma	102-104
Cataracts	105
Prostatic Hypertrophy	106-108
Psoriasis	109
Healthspan	25,38,59
Lifespan	25,38,59

Table 1. Conditions with emerging evidence for a causal contribution of cellular senescence or that are alleviated by senolytic drugs. Cellular senescence contributes to age-related dysfunction and diseases throughout the lifespan. Senescence can contribute to local and systemic inflammation, dysfunction, and spread of senescence through release of cytokines, chemokines, proteases, ferritin, stem cell/progenitor toxins, reactive metabolites. miRNA's, mitochondrial DNA, other nucleotides, and extracellular vesicles, the SASP. Pre-senescent cells, which have limited remaining replicative potential, and senescent cells, which cannot replicate, accumulate to a greater extent in vivo in skin biopsies from older than younger subjects9. Senescent and pre-senescent adipocyte progenitors cloned from adipose tissue increase with aging in rats raised under controlled conditions. Senolytics have been shown to alleviate many of these conditions by us (bold) and others.

Most studies of senolytics for various disease states, including in humans, have been with D+Q since D and Q were the first senolytics discovered. However, while D+Q is relatively safe, it is likely not as safe as Fisetin for very ill patients. Unlike Fisetin, D cannot be administered safely to patients with a prolonged QTc (>450 msec). Many elderly and chronically-ill nursing home residents have a prolonged QTc, meaning they would be excluded from studies involving treatment with D. Additionally, there are multiple other drug interactions with D that would result in fewer patients being able to be treated than with Fisetin. Navitoclax has a poorer safety profile than Fisetin or D+Q: unlike D, which was approved by the FDA in 2006,

Navitoclax has failed to gain FDA approval so far as a generally-available prescription drug, largely because of extensive and unpredictable induction of apoptosis in non-senescent cell types — "panolytic effects". For example, Navitoclax can cause life-threatening neutropenia or hemorrhage due to platelet depletion. Fisetin so far has had an exceptional safety profile in our clinical trials for elderly patients with multi-morbidity. Therefore, we decided to analyze Fisetin here rather than D+Q or Navitoclax.

"Hit and run": D+Q or Fisetin are effective if administered once every few days or weeks since they do not need to be continuously present to occupy a receptor or interfere with an enzyme, reducing off-target effects (Figs. 28&29). Brief disruption of pro-survival pathways is sufficient to kill senescent cells in mouse and human cell cultures, *in vivo* in mice and monkeys, and in

human adipose explants freshly-isolated from obese subjects 15,38,59,64. In mice, monthly D+O is as effective as daily administration to alleviate age-related osteoporosis, reducing potential side-effects. These points, together with satisfying a modified set of Koch's postulates (Table 2), show that senolytics alleviate dysfunction by removing senescent cells, not other off-target mechanisms. Unlike microbes or cancer cells, since senescent cells do not divide, they are unlikely to acquire replication-dependent drug resistance. Fisetin is well-suited for a "hit-andrun" administration protocol since it has an elimination T½ of ~3 hours, we demonstrated that it takes only 30 minutes of exposure of human tissues for senolytics to initiate the apoptosis process, and senescent cells take over 1 week to re-accumulate. Of note, no steady state levels for Fisetin need to be achieved and the goal is to eliminate senescent cells in a "hit-and-run" fashion, not to achieve a steady state blood level. The critical outcome here is target engagement, i.e., do we kill senescent cells?, not do we achieve a particular drug or tissue level? Therefore, as in our other trials, traditional blood pharmacokinetic parameters will not be assayed. Rather, the critical pharmacodynamic measure, senescent cell abundance, will be assayed. This approach has been tacitly agreed to by the FDA regarding our other clinical trials of senolytics, including with Fisetin.

